4.0 Study Measures

4.1 Study Site Characteristics

Study site characteristics consist of counts of all-cause admissions, skin infections, pneumonia, diabetic foot infection, and infective endocarditis recorded at each site. These will be collected in paper admission logs monthly or bimonthly from the sites. These will be entered into an Excel spreadsheet by Mapi’s Clinical Operations team, which will then be brought into [REDACTED] for analysis.

4.2 Baseline Characteristics

The following baseline characteristics will be collected:

- **Demographic data:** Age (in years, derived and described in Appendix B), gender, ethnicity, race, employment status, and location patient presents from (e.g. from home, long-term care [LTC], skilled nursing facility [SNF], nursing home).
- **Comorbidities:** Morbid obesity (derived and described in Appendix B), myocardial infarction, congestive heart failure, peripheral vascular disease, cerebrovascular disease, dementia, chronic pulmonary disease, rheumatologic disease, peptic ulcer disease, mild liver disease, diabetes with/without complications, renal disease, moderate or severe liver disease (Child-Pugh Class B and C), any malignancy (including leukemia and lymphoma), metastatic solid tumor, cancer (active, remitted/cured), alcohol/drug abuse/illicit needle use, malnutrition,

human immunodeficiency virus, other immuno-compromising conditions, altered mental status, lymphedema or chronic venous stasis, and peripheral vascular disease.

- **Charlson Comorbidity Index (CCI):** A derived variable based on the presence/absence of the comorbidities specified above. The formula by which the CCI is calculated is detailed in Appendix C.
- **Infection type:** Cellulitis/erysipelas, wound infection, major cutaneous abscess
- **Infection and clinical characteristics during the initial assessment in the ED:**
 - Lesion size and location
 - Fever (>100.4°F; >38.0°C; or site-specific definition)
 - *Systemic inflammatory response syndrome (SIRS)* (see Appendix B)
 - Blood pressure (BP, in mmHg)
 - Serum creatinine (mg/dL)
 - C-reactive protein (mg/dL)
 - Rapid microbial assay
 - Microbiological culture type (i.e., blood, wound swab, urine) and results thereof
 - Presence of recurrent infection and/or any ABSSSI infections in the prior 6 months
- **Utilization of healthcare services in prior 3 months:** Hospitalizations and primary reason, surgical interventions and primary reason, admission to the ICU and primary reason, ED visits or other outpatient visits (e.g., infusion center and physician's office) and primary reason, use of dialysis, use of any medications for chronic diseases and specifically use of an antibiotic medication, prior antibiotic treatment failure (determined by discontinuation of treatment due to worsening or recurrent ABSSSI or the occurrence of an adverse event related to the antibiotic), and receipt of wound care for the presenting infection. The utilization will be based on examination of the patient's medical records.

4.3 Primary Outcome

The primary outcome (hospital admission rate) will be assessed during the initial episode of care.

[figure not shown]
4.4 Secondary Outcomes

[figure not shown]
[figure not shown]
Secondary outcomes will be assessed during initial care (the date of enrollment to day 14) and/or follow-up (30 days after initial care), and include:

[figure not shown]
[figure not shown]
Measure	Definition	Period of Assessment
Total admitted hospital days	Total LOS during the 44 days of the study (including initial hospitalization)	Initial care and follow-up
Infection-related total admitted hospital days	Total LOS of all infection related hospitalizations during the 44 days of the study (including initial hospitalization)	Initial care and follow-up
ED LOS	Time spent in ED in hours from triage to release (either admitted to the hospital, admitted to observation, or released to home)	Initial episode of care
Infection-related major surgical interventions that required operating room time	Number of all, unexpected and expected infection-related major surgical interventions that required operating room time	Initial care and follow-up
Infection-related hospitalizations	Number of infection-related hospitalizations	Initial care and follow-up
Infection-related hospitalizations that resulted in admission to intensive care unit (ICU)	Number of infection-related hospitalizations resulting in admission to the ICU.	Initial care and follow-up
All cause hospitalizations in the 30 days following discharge from the initial hospitalization or release from the initial ED visit (if not hospitalized)	Number of all hospitalizations for patients discharged from the ED and re-hospitalizations for patients who had an initial hospital admission	Overall, including Initial care and follow-up
Infection-related ED visits	Number of all, unexpected and expected infection-related ED visits	Initial care and follow-up

Measure	Definition	Period of Assessment
Infection-related outpatient healthcare visits (e.g., physicians' office visits, ED visits, infusion center visits, home health visits)	Number of all, unexpected and expected infection-related outpatient healthcare visits, generated for all patients and repeated by site.	Initial care and follow-up
Use of PICC line or central line to administer antibiotic therapy	Number of PICC line or central line placement for antibiotic therapy	Initial care and follow-up
Infection-related healthcare visits (e.g., hospitalizations, ED visits, other outpatient visits) due to PICC line or central line used to administer antibiotic therapy	Number of all, unexpected and expected infection-related healthcare visits due to PICC line or central line used to administer antibiotic therapy	Initial care and follow-up
Serious adverse events (SAEs)	Number of events, number of patients and percentage of patients experiencing SAEs as described in protocol	Initial care and follow-up
Patient satisfaction with care	Summarize patient satisfaction with care (reported by patient, questionnaire provided in protocol). This will be completed by a caregiver if the patient cannot complete.	Follow-up
Patient work and productivity loss	Number of days with lost/reduced productivity, as measured through the Work Productivity and Activity Impairment (WPAI) questionnaire. This will be completed by a caregiver if the patient cannot complete.	Follow-up

Measure	Definition	Period of Assessment
Patient HRQoL	Patient reported, as measured through the SF-12 ¹ (short-form), with acute recall (1-week recall). This will be completed by a caregiver if the patient cannot complete.	Initial care (in person) and follow-up (over phone). Change scores calculated for initial care

4.7 Safety

At each visit, patients will be queried regarding adverse events (AEs) and SAEs, and medication errors that occurred since the previous visit. Specifically, patients will be asked to volunteer information with a non-leading question

such as, "How do you feel since your last visit?" Study site personnel will record all pertinent information in the patient's case report form (CRF), as described in details in the protocol.

5.0 Changes in the Protocol Specified Analyses

Infection characteristics described in the protocol including hyperglycemia (>120mg/dL blood glucose or site-specific definition), thrombocytopenia (<150,000 platelet count or site-specific definition), acidosis (<7.35 pH of the blood or site-specific definition or described in medical chart), hyponatremia (<135 mEq/L blood sodium or site-specific definition), uremia (as described in medical chart), and anemia (14-18 g/dL hemoglobin for men or 12-16 g/dL hemoglobin for women or site-specific definition) will not be derived from laboratory values or reported in analysis.

An interim analysis was performed after the enrollment of approximately 75 patients to evaluate the original sample size. It was determined a sample size greater than 322 would be needed for hypothesis testing of the primary outcome of total number of days spent in the hospital. Factors that contributed to the large sample size include:

- The observed variation was larger than the original estimate (SD = 3.0 days).
- The observed attrition rate was larger than the original assumption (10%).

Additionally, the observed mean total LOS was much smaller than the protocol assumption (4.0 days). It was determined that observing a statistically significant reduction in the total number of days spent in the hospital in the post-period was unlikely.

Based on results of the interim analysis, an adjustment was made at the time of the analysis to revise the primary outcome from total admitted hospital days to hospital admission rate at initial episode of care. The initially estimated final enrollment of 322 subjects, including adjustments for attrition, would support one-sided hypothesis testing (two-sample Pearson chi-square test for proportion difference with equal group weights using a normal approximation) with a significance level of 0.05 and at least 80% power assuming hospital admission rate comparing the pre- and post-periods were 38% versus 23%. This change has been reflected in the protocol, Amendment Version 3.0.

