6.1.2 Sample size

Hospital admission rate, which is correlated to total hospital time for the study population, was largely unknown for purposes of sample size estimation. The final enrollment to support hypothesis testing for a primary outcome of total admitted hospital days was initially calculated as 322 subjects (161 subjects in each period). The sample size was evaluated after a planned interim analysis of pre-period data once 75 subjects were enrolled in the pre-period. Based on results of the interim analysis, an adjustment was made at the time of the analysis to revise the primary outcome from total admitted hospital days to hospital admission rate at initial episode of care. The initially estimated final enrollment of 322 subjects, including adjustments for attrition, would support one-sided hypothesis testing (two-sample Pearson chi-square test for proportion difference with equal group weights using a normal approximation) with a significance level of 0.05 and at least 80% power assuming hospital admission rate comparing the pre- and post-periods were 38% versus 23%.

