6.2.5.2 Secondary Outcomes

Secondary Outcomes: Total Number of Days Spent in Hospital

Total number of days spent in the hospital will be calculated by two methods for the FAS population. First, LOS will be calculated by inpatient stays only and second, LOS will be calculated by inpatient stays including time spent in prolonged observation status (>1 day). Descriptive statistics for total number of days spent in hospital will be shown in a table by initial care, follow-up, and overall for the pre-period and post-period, and depicted graphically overall using box plots. Patient counts and percentages will be given for the primary outcome (e.g., 0 day, 1 day ... > 5 days). Descriptive statistics in the table will be repeated by patients who complete the study or are admitted for comparison. No formal hypothesis testing will take place.

Secondary Outcomes: Infection-Related Total Admitted Hospital Days

Infection-related total admitted hospital days will be calculated by two methods by the pre-period and post-period for the FAS population. First, LOS will be calculated by inpatient only stays and second, LOS will be calculated by inpatient stays including time spent in prolonged observation status (>1 day). The infection-related total admitted hospital-days will be assessed using a similar approach described for the primary analysis and will limit to patients who had infection-related hospital stays. Tables will reflect descriptive statistics for infection-related hospital stays and depicted graphically overall using box plots. Summaries will be repeated for only patients that are admitted. No formal hypothesis testing will take place.

Secondary Outcomes: ED Length of Stay at Initial Episode of Care

Tables will reflect descriptive statistics for ED length of stay at the initial episode of care by the pre-period and post-period for the FAS population. No formal hypothesis testing will take place.

Secondary Outcomes: Infection-Related Major Surgical Interventions that Required Operating Room Time

Infection-related major surgical interventions that required operating time will be displayed in tables by initial care, follow-up, and overall by the pre-period and post-period for the FAS population. Patient counts and percentages will be reported for no, any, expected, and unexpected surgical interventions. No formal hypothesis testing will take place.

Secondary Outcomes: Infection-Related Hospitalizations

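### The primary outcome was replaced after a planned look at about 75 pre-period patients who stay in the comparator; a sensitivity analysis without them is needed

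*SAP*

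**What the plan says.** SAP 6.1.2 (and Protocol 5.3) describes the look: "The sample size was evaluated after a planned interim analysis of pre-period data once 75 subjects were enrolled in the pre-period". SAP 5.0 lists what it found: more variation than the assumed SD of 3.0 days, more attrition than the assumed 10%, and a mean stay well below the assumed 4.0 days. More than 322 patients would be needed, and "It was determined that observing a statistically significant reduction in the total number of days spent in the hospital in the post-period was unlikely". In response, "an adjustment was made at the time of the analysis to revise the primary outcome from total admitted hospital days to hospital admission rate" at the initial episode of care. Enrollment stayed at 322, now justified by 38% versus 23% at one-sided 0.05 with at least 80% power.

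SAP 6.1.1 puts every enrolled pre-period patient with at least one antibiotic dose into the full analysis set. Nothing there or in SAP 6.2.6.1 separates the interim patients. For total hospital days, SAP 6.2.5.2 gives descriptive statistics and says "No formal hypothesis testing will take place".

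**The concern.** The look was planned to check sample size, and neither document gives a rule under which it could change the outcome. The new outcome was adopted when its values in about 75 comparator patients may have been available, and those patients then help to set the rate that the pathway has to beat. If the admission rate was chosen partly because it looked high enough to reduce, a chance-high interim value carries into the final pre-period rate and moves the contrast towards the pathway. The look covered only pre-period patients, but that does not remove this route to bias, because the pre-period is the comparator.

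As planned, the report will not show whether the primary result depends on the patients whose data prompted the switch. The outcome that was replaced has no definite between-period comparison.

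**Working it through.** **Inputs.** 161 per period, 38% versus 23%, one-sided 0.05, Pearson chi-square with normal approximation (SAP 5.0, 6.1.2); 75 interim patients (SAP 6.1.2; SAP 5.0 and 6.1.6 say approximately 75). Share of comparator: 75/161 = 46.6%. Remaining pre-period patients: 161 − 75 = 86. All 75 are assumed to meet the full-analysis-set rule.

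**1. The plan's power figure.** Power = Φ{[(p1 − p2) − 1.645·s0]/s1}, where s0 = √[p̄(1 − p̄)(1/n1 + 1/n2)] and s1 = √[p1(1 − p1)/n1 + p2(1 − p2)/n2].

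- 161 v 161: p̄ = 0.305, s0 = 0.0513, s1 = 0.0506; (0.15 − 0.0844)/0.0506 = 1.296, so power is 90.2%.
- 10% attrition, 144 v 144: 87.2%.
- 80% power needs 116 per period, so the stated figure holds up to 1 − 116/161 = 28% attrition.

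The stated power is reproduced, so the point is not about the arithmetic.

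**2. Type I error when the 75 are kept.** With no pathway effect and a common true rate p, let X0 ~ Bin(75, p), X1 ~ Bin(86, p) and X2 ~ Bin(161, p). Reject when [(X0 + X1)/161 − X2/161] / √[p̂(1 − p̂)·2/161] > 1.645, where p̂ is the pooled rate. Exact enumeration gives three cases.

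- Switch unrelated to the interim admission rate: 4.9 to 5.1% for true rates from 23% to 43%.
- Switch made only if X0/75 ≥ p: column A below.
- Interim count fixed at 28 or 29 of 75 (37.3% or 38.7%), on the assumption that the 38% design value was the interim rate: columns B and C.

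| True rate | A: interim rate ≥ true rate | B: 28/75 | C: 29/75 | 75 excluded |
|---|---|---|---|---|
| 30% | 8.8% | 13.2% | 16.3% | 5.1% |
| 33% | 8.6% | 7.8% | 9.8% | 5.2% |
| 35% | 8.9% | 5.1% | 6.6% | 5.2% |
| 38% | 8.5% | 2.6% | 3.4% | 5.1% |
| 40% | 8.2% | 1.6% | 2.2% | 5.1% |

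The 95% interval for 28 to 29 of 75 is roughly 27% to 50%, so every true rate in the table is compatible with such an interim result. Columns B and C run in both directions: error is above nominal if the interim rate was chance-high, and below it if the interim rate was accurate or chance-low.

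**3. Power without the 75.**

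- 86 v 161: p̄ = (86 × 0.38 + 161 × 0.23)/247 = 0.282, s0 = 0.0601, s1 = 0.0620; (0.15 − 0.0989)/0.0620 = 0.825, so power is 79.5%.
- 10% attrition, 77 v 144: 75.6%.

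**The case against.** The look was planned, used pre-period data only, and is disclosed in Protocol 5.3 and in SAP 1.0, 5.0, 6.1.2 and 6.1.6. The reasons given for dropping hospital days are its SD, its mean and attrition; the admission rate is not among them. This stands, and it rules out three stronger readings.

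- *The outcome was switched on an observed treatment effect.* Nothing shows that a pre/post difference was seen.
- *The true error rate is 13 to 16%.* That needs 38% to be the interim rate and the interim rate to be about 8 points too high. The documents say neither. SAP 6.1.2 calls the admission rate largely unknown for sample size estimation. SAP 7.0 marks the admission-rate table as output that can be produced at interim and as minimum output for sample size confirmation. That makes it plausible that the rate was seen, but does not establish it. The separate interim report (SAP 6.1.6) would settle the matter.
- *Readers will not be able to judge the original outcome.* SAP 6.2 and 6.2.5.2 already provide means with 95% CIs, SDs and medians by period, plus box plots. Between-period differences with intervals are planned, though only conditionally. A p-value on an outcome already judged underpowered would add little.

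What remains is that disclosure tells readers that the switch happened, not whether the result depends on the patients behind it.

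**Conclusion.** The concern holds as a possible selection bias that the plan leaves unexamined. It is not a demonstrated inflation of error. One-sided type I error is near 5% if the switch did not depend on the interim admission rate, and about 8.5 to 9% (true rates of 30 to 38%) if it was made only when that rate was at or above its true value. If 28 or 29 of the 75 were admitted, which is an assumption, conditional error runs from about 2% (true rate 40%) to 13 to 16% (true rate 30%). The documents do not show which case applies. These figures assume 161 analysed per period, independent patients and a common admission rate across sites. The issue does not invalidate the primary analysis, but a check that is cheap and close to nominal in every case examined should be in the SAP.

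**What to change.** 1. Keep the primary analysis. In SAP 6.2.6.1, add a sensitivity analysis of hospital admission rate that excludes the interim pre-period patients, with the same test, reported beside the primary result.
2. In SAP 5.0, state whether the interim admission rate was seen before the outcome was changed, and whether 38% came from it.
3. In SAP 6.2.5.2, make the between-period difference in total admitted hospital days with its 95% CI a definite output, labelled as the original primary outcome. A p-value is optional.

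The cost is two rows of output and a sentence or two, from data already being collected. The sensitivity analysis has less power: about 80% for 38% versus 23% with no attrition and about 76% at 10%, and SAP 5.0 reports attrition above 10%. The 75 are also the earliest enrollees, and SAP 3.0 lets sites move to the post-period at different times. Excluding them therefore shifts calendar time and possibly site mix, so a changed result would call for caution but would not by itself prove selection at the interim.

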6.0 Statistical Plan and Methods

As the data are analyzed, some deviations from expectations and/or assumptions will become apparent (e.g., missing data, distributional assumptions, and small sample sizes in some subgroups of interest). In

instances where these deviations would make the proposed analyses inappropriate/infeasible and/or difficult to interpret, modifications to the analysis plan will be made accordingly, and noted in the final report.

6.1 General Considerations

6.1.1 Analysis populations

Enrolled Set

The enrolled set consists of all patients who have signed informed consent and met all study eligibility criteria. Data will be summarized on disposition and baseline characteristics. Output will be summarized by study period (pre-period vs. post-period). All data listings will be reported for the enrolled set unless specified in Section 5.2.

Full Analysis Set

The full analysis set (FAS) population consists of all enrolled patients. Additionally, patients in the pre-period must receive at least one dose of antibiotics and patients in the post-period must receive at least one dose of dalbavancin for inclusion. All patients in the pre-period and post-period will be analysed. Data will be summarized by study period.

Data from all patients will be aggregated across sites, and all analyses related to protocol outcomes and baseline characteristics will be undertaken on the aggregate pre- and post-periods.

